APPENDIX A

Table 2. Study Visit and Assessment Schedule for PCP Participants

	Screen Visit	Pre-Study Session	Weeks 1-6	Week 7	Week 8	Weekend Retreat	Post-Study Session	Months 1-30	Post-Study Session	Duration (min)
Group 1 Participants: MBSR and Mindful Communication										
Email or Phone Screen Interview	X									
Informed Consent										
Informal Consent Form*		X								20
Informal Consent Opt*		X								20
Baseline History										
Demographic Survey*		X								5
MBSAQ-PC*		X								8
Survey of meditation experience†		X								8
Weekly Mindfulness Practice Diary			X	X	X		X	X	X	29
Mindfulness Self-Report History										
MMQ2*		X					X		X	30
SCS-5P*		X					X		X	4
Clinical Assessment History										
DRG-2.1*		X					X		X	9
PSY*		X					X		X	9
Provider Resilience History										
Morlock Burnout Inventory*		X					X		X	4
Workplace Wellbeing Scale*		X					X		X	4
Johnson Scale of Empathy (JSE)*		X					X		X	5
Johnson Career Reporting							X		X	5
Group 1a										
MBSR Course			X	X	X					1200
7.5-hour mindfulness retreat				X						480
Group 1b										
14-hour intensive mindfulness retreat						X				1080
Group 1c										
Mindful Communication Course							X	X		1800
Visit Duration (min)	20	80	80	80	150	1080	80	180	60	
Group 2 Participants: No Training										
Email or Phone Screen Interview	X									
Informed Consent										
Informal Consent Form*		X								20
Informal Consent Opt*		X								20
Baseline History										
Demographic Survey*		X								5
MBSAQ-PC*		X								5
Survey of meditation experience†		X								8
Weekly Mindfulness Practice Diary							X		X	26
Mindfulness Self-Report History										
MMQ2*		X					X		X	30
SCS-5P*		X					X		X	4
Clinical Assessment History										
DRG-2.1*		X					X		X	9
PSY*		X					X		X	9
Provider Resilience History										
Morlock Burnout Inventory*		X					X		X	4
Workplace Wellbeing Scale*		X					X		X	4
Johnson Scale of Empathy (JSE)*		X					X		X	8
Johnson Career Reporting							X		X	5
Visit Duration (min)	20	80	0	0	0	0	80	0	60	
* Represents surveys and/or instruments administered through REDCap.										

Table 3. Study Visit and Assessment Schedule for Patient Participants

	Screen Visit	Consent Session	Pre-Treatment Surveys	Group Orientation	Week 1-5	Week 6-7	Action Plan	Week 8
Patient Screening								
Patient Eligibility Questionnaire	X							
MINDFUL-PC Patient Screening Form [#]	X							
Informed Consent								
Informed Consent Form		X						
Consent Quiz		X						
REALM-SF [%]		X						
Baseline Battery								
Demographics Survey [#]			X					
SMME [#]			X					
FTND [#]			X					
Mindfulness Self-Report Battery								
FFMQ [#]			X					
SCS-SF [#]			X					
DERS [#]			X					
MAIA [#]			X					
Clinical Assessment Battery								
DASS-21 [#]			X					
PHQ-2 [#]			X					
PSS [#]			X					
AUDIT-C [#]			X					
DSM-V SSU [#]			X					
PROMIS-ASF [#]			X					
PROMIS-DSF [#]			X					
Self-Management Battery								
SECD-6 [#]			X					
PAM [#]			X					
PCQ [#]			X					
APA-10 [#]							X	
APIS-5 [#]								
Action Plan Worksheet							X	
TFEQ-R18			X					
Weekly Mindfulness Practice								
Weekly Mindfulness Practice Diary					X	X		X
Weekly Mindfulness Resources Use Survey					X	X		X
MTPC Satisfaction Survey								
Satisfaction survey [#]								
Engagement and Adverse Event Reporting								
Adverse Event Reporting Form								
Participant Engagement Phone Call					X	X		X
Patient Study Visits								
60-minute Group Orientation				X				
2-hour MTPC Sessions					X [^]	X [^]		X [^]
Action Plan Study Session							X	
7-hour Full-Day Session						X [^]		
Action Plan Interview								
Visit Duration (min)	10	32	83	60	660[^]	684[^]	20	132[^]
Payments at study visits (\$)			20					
[^] Represents surveys, events, and time durations that only apply to MTPC group participants [%] Represents surveys administered only to patients who score below 90% on the ICF assessment [#] Represents surveys and/or instruments administered through REDCap [*] Represents surveys, events, and time durations that only apply to 6-month waitlist participants								

Table 3 (Cont'd). Study Visit and Assessment Schedule for Patient Participants

	Post-Treatment Surveys	Week 9	Week 10	Week 16	Follow-up Surveys	Optional Action Plan Interview	Item Duration (min)
Patient Screening							
Patient Eligibility Questionnaire							5
MINDFUL-PC Patient Screening Form [#]							5
Informed Consent							
Informed Consent Form							20
Consent Quiz							10
REALM-SF [%]							2
Baseline Battery							
Demographics Survey [#]							5
SMME [#]							5
FTND [#]							3
Mindfulness Self-Report Batter							
FFMQ [#]	X				X		8
SCS-SF [#]	X				X		4
DERS [#]	X				X		5
MAIA [#]	X				X		5
Clinical Assessment Batter							
DASS-21 [#]	X				X		3
PHQ-2 [#]							1
PSS [#]	X				X		3
AUDIT-C [#]	X				X		1
DSM-V SSU [#]	X				X		3
PROMIS-ASF [#]	X				X		3
PROMIS-DSF [#]	X				X		3
Self-Management Battery							
SECD-6 [#]	X				X		3
PAM [#]	X				X		4
PCQ [#]	X				X		3
APA-10 [#]							4
APIS-5 [#]	X	X	X	X	X		3
Action Plan Worksheet							
TFEQ-R18	X				X		5
Weekly Mindfulness Practice							
Weekly Mindfulness Practice Diary	X				X		6
Weekly Mindfulness Resources Use Survey	X				X		6
MTPC Satisfaction Survey							
Satisfaction survey [#]	X [^]						5
Engagement and Adverse Event Reporting							
Adverse Event Reporting Form	X				X		2
Participant Engagement Phone Call							5
Patient Study Visits							
60-minute Group Orientation							60
2-hour MTPC Sessions							960 [^]
Action Plan Study Session							20
7-hour Full-Day Session							420 [^]
Action Plan Interview						X	
Visit Duration (min)	85	3	3	3	92	30	
Payments at study visits (\$)	40				80	15	
[^] Represents surveys, events, and time durations that only apply to MTPC group participants [%] Represents surveys administered only to patients who score below 90% on the ICF assessment [#] Represents surveys and/or instruments administered through REDCap							

* Represents surveys, events, and time durations that only apply to 6-month waitlist participants

Table 4. Study Visit and Assessment Schedule for HEART pilot study participants

Concurrent Cohort:

	Infomed Consent	1st Behavioral Visit (Wk 0)	Part 0 (Wk 0)	Part 1 (Wks 5 & 6)	Part 2 (Wks 7 & 8)	2nd Behavioral Visit (Wks 8-9)	Item Duration (min)
Informed Consent Session	x						30
Smartphone app/accelerometer-based daily activity tracking			daily	daily	daily		2
FAST Questionnaire			daily	daily	daily		10
Daily mindfulness practice diary			daily	daily	daily		3
Daily mindfulness resource use diary			daily	daily	daily		2
Behavioral Measures		x				x	20
Visit Duration (min)	45	45	15/day	15/day	15/day	45	
Payments at study visits (\$)		\$30			\$105	\$60	\$195

Table 5. Study Visit and Assessment Schedule for fMRI Pilot Study Participants

	Screening	fMRI session 1	fMRI session 2	Item Duration (min)
Group Scheduling phone screen call				
fMRI pilot screening form	x			5
Edinburgh Handedness Questionnaire	x			5
fMRI appointment				
Informed Consent Form		x		20
Toxicology/Pregnancy screening		x	x	10
Autonomic measures electrodes/belt set-up		x	x	10
fMRI scan		X	X	90

fMRI questionnaire		X	X	5
Visit Duration (min)	10	110	110	
Payments at study visits (\$)		5 + 50	5 + 50	
Travel Expenses (\$)		10 or parking	10 or parking	

Choice of Smartphone Applications and Tracking Devices

The HEART Pilot study is intended to test the feasibility of using commercial behavior tracking smartphone applications and devices in the context of the action planning and initiation process of the MINDFUL-PC study, as well as to validate with objective behavioral measures, the self-report action plan initiation survey. We are not pilot testing the devices and applications themselves but are pilot testing their use in our studies. Due to the rapid innovations in the consumer market, we have left open the possibility of using other, improved but similar applications for activity, sleep, and diet tracking. The Argus App is among the current best possible apps for this purpose. Below is a list of similar alternatives.

We are considering the following smartphone activity tracking applications for inclusion in the study as alternatives to the Argus App:

- Pedometer for Android
- Stepz for IOS.
- Activ8 by 2M Engineering

We are considering use of the following activity tracking devices for inclusion in the study:

- Fitbit
- Moov
- Jawbone
- Withings
- MD2K Cerebrum
- Garmin Vivosmart

1. Bornemann, B. and T. Singer, *Taking time to feel our body: Steady increases in heartbeat perception accuracy and decreases in alexithymia over 9 months of contemplative mental training*. *Psychophysiology*, 2017. **54**(3): p. 469-482.
2. Hendrickson, K.L. and E.B. Rasmussen, *Effects of mindful eating training on delay and probability discounting for food and money in obese and healthy-weight individuals*. *Behav Res Ther*, 2013. **51**(7): p. 399-409.
3. Ashe, M.L., M.G. Newman, and S.J. Wilson, *Delay discounting and the use of mindful attention versus distraction in the treatment of drug addiction: a conceptual review*. *J Exp Anal Behav*, 2015. **103**(1): p. 234-48.
4. Morrison, A.B., et al., *Taming a wandering attention: short-form mindfulness training in student cohorts*. *Front Hum Neurosci*, 2014. **7**: p. 897.
5. Guck, T.P., et al., *Attributions regarding unmet treatment goals after interdisciplinary chronic pain rehabilitation*. *Clin J Pain*, 2008. **24**(5): p. 415-20.
6. Margolin, A., et al., *A controlled study of a spirituality-focused intervention for increasing motivation for HIV prevention among drug users*. *AIDS Educ Prev*, 2006. **18**(4): p. 311-22.
7. Arozullah, A.M., et al., *Development and validation of a short-form, rapid estimate of adult literacy in medicine*. *Med Care*, 2007. **45**(11): p. 1026-33.

REFERENCES

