4. Revise analytic methods to include the more robust and flexible mixed methods analysis

Version 1.13: Version Date: (September 29, 2017)

1. Add one research assistant ([name])

Version 1.14: Version Date: (October 19, 2017)

1. Add two research assistants ([name] and [name])

Version 1.15: Version Date: (November 17th, 2017)

1. Add research Assistant ([name])
2. Add engagement calls for alumni cohort of HEART study protocol
3. Add engagement calls for alumni cohort of HEART study informed consent form

Version 1.16: Version Date: (December 18th, 2017)

1. Add action plan interview for MINDFUL-PC completers
2. Add action plan interview to MINDFUL-PC patient informed consent form
3. Add payment of \$15 for action plan interview.

Version 1.17: Version Date: (January 11th, 2018)

1. Remove daily diet picture tracking with a mobile app from the HEART study measures.
2. Remove daily sleep tracking with a mobile app from the HEART study measures
3. Remove ASA24 from HEART study measures

4. Add “Food, Activity, and Sleep Tracking (FAST) Questionnaire” to HEART study measure.
5. Adjust HEART pilot study payment structure to match modifications to health behavior tracking activities
6. Add 3-Factor Eating Questionnaire-R18 as a study measure to MINDFUL-PC patient participant battery

Version 1.18: Version Date: (March 6, 2018)

1. Add [name] to protocol

Version 1.19: Version Date: (April 12, 2018)

1. Add Behavioral Measures study visit to HEART Study, and modify HEART Study Informed Consent Form and payment structure accordingly. Behavioral Measures consists of 3 tasks: (Sustained Attention Response Task (SART), Heartbeat Detection Task (HBDT), and 5-Trial Adjusting Delay Hypothetical Discounting Task (HDT).
2. Remove alumni cohort from HEART Study informed consent form and alter the definition of concurrent cohort to include MINDFUL-PC participants who are joining an MTPC group after being in the LDC.
3. Modify Weekly Mindfulness Practice Diary to indicate how blanks will be treated by adding one line that states, “If you leave any field blank we will treat this as a “0” or “No”
4. Add to MINDFUL-PC patient demographics survey optional sections that ask about gender and sexual identity in order to ensure adequate access and representation among underrepresented populations.

Version 1.20: Version Date (May 18, 2018)

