7. Current meditation or intense yoga practice of more than 30 min a week or meditation experience of more than 20 hours in the past 10 years. (Since this pilot is focused on investigating mechanisms, we will limit the sample to participants who are new to mindfulness techniques). (Assessed before the phone-screening using the main study database.)
8. Participants with body weight >230 lbs or BMI > 38 will require additional in-person screening and PI approval, because of potential tight fit in the MRI scanner. (Assessed during the phone-screening.)
9. Participants with vascular disease, such as peripheral vascular disease, varicose veins, or lymphedema, in both lower limbs. (Participants may be included with PI approval, if they have vascular disease only in the right limb, which will not receive cuff-pain stimulation and no signs of disease in the left limb.) (Assessed during the phone-screening.)

10. Based on clinical judgment and safety assessment by the PI, the participant is inappropriate for fMRI or unable to complete experiments. (Assessed only if after the phone-screening and other interactions with the patient, the study personnel has doubts about the patients' ability to participate in this additional study.)

C.1.c.3. Patient Participant HEART Pilot Additional Inclusion Criteria:

1. Participant must be currently enrolled in, or have completed, the MINDFUL-PC study.
2. Participant must have access to a smartphone that is compatible with the activity tracker application.
3. Participant must be willing to use the smartphone application and/or wear a wristband activity tracker every day for activity monitoring periods of the HEART study and be willing to take pictures of their food and drink intake.
4. Participant must be able to fill out the study questionnaires daily on a computer or compatible mobile device.

Screening will be conducted by study staff and research assistants. Decisions on the inclusion/exclusion will be made by the study staff under the supervision of the neuroimaging postdoctoral fellow and Principal Investigator in cases where no additional clarifications are needed. In cases where MRI safety needs further assessments, the postdoctoral fellow or imaging consultants at the Martinos Center for Biomedical Engineering will coordinate the assessment with the MRI physics staff at the Martinos Center, and will decide on inclusion or exclusion of the participant.

C.2. Recruitment:

C.2.a. PCP Recruitment:

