At the end of the MINDFUL-PC orientation, participants who express interest in participating in the HEART study will be scheduled by one of the research assistants to come for an in person 45-minute Behavioral Measures visit, which will be conducted on an individual basis. In this visit participants will complete three behavioral measures tasks, install any required smartphone applications, be introduced to wristband activity trackers if applicable, and be given a chance to ask any questions. Participants are reminded that they will repeat the Behavioral measures visit once more during weeks 8-9 of the study.

HEART Pilot Study Sessions:

Concurrent Cohort:

Timing: HEART study participants participating in the **concurrent cohort** will complete the behavioral tasks 1 week prior to MTPC Session 1 of the intervention (Part 0) (applies to both waitlist and intervention arms), and will complete daily behavioral tracking surveys during Part 0, and for 4 weeks starting at MINDFUL-PC Study Week 5 (Parts 1 and 2). Part 1 is study weeks 5-6, and Part 2 is Study Weeks 7-8. Participants will complete the second behavioral tasks visit between Study Weeks 8 and 9.

Inclusion/Exclusion criteria: Participants must either be newly enrolling in the MINDFUL-PC study or be joining a MINDFUL-PC primary care group after having completed their 6-month study requirements in the low-dose comparator group. Participants must have access to a smartphone that is compatible with the activity tracking application, participants must be willing to attend the two behavioral task sessions, to use the smartphone application and/or wristband tracking device each day during the study collection periods, and participant must be willing to fill out online surveys at home.

HEART Study Tasks: Participants will do the following tasks on a daily basis for the duration of the HEART study:

- **Mindfulness Practice Diary:** Fill out the MINDFUL-PC weekly mindfulness practice diary and resource use diary daily for 1 week prior to MTPC Session 1 of the intervention and then for 4 weeks during Weeks 5 through 8.

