Food, Activity, and Sleep Tracking (FAST) Questionnaire: Participants will be asked to fill out a daily questionnaire about their food, activity, and sleep tracking. The survey is adapted from the Automated Self-Administered 24-Hour Dietary Assessment Tool (ASA24) and the National Sleep Foundation Sleep Diary.

The ASA24 was released in 2009 by the NIH and the National Cancer Institute as a web-based tool that enables multiple, automatically coded, self-administered 24-hour recalls. This tool was designed for use by research participants, clinicians, patients, and students. The ASA24 asks detailed questions about food form, preparation, portion size, and additions using an extensive branching logic database. The ASA24 was designed to be culturally sensitive and accessible by individuals using assistive technologies. Features of the ASA24 respondent website can be found here (<https://epi.grants.cancer.gov/asa24/respondent/features.html>). A demo version of the respondent site can be found here (<https://asa24.nci.nih.gov/demo/>).

The FAST Questionnaire asks participants what time they went to bed, what time they got out of bed, the total hours slept, any naps taken during the day, then about the timing and amount of alcoholic and caffeinated drink consumption. It also asks if they exercised throughout the day and then further asks how long they performed each type of exercise.

The food tracking portion asks subjects what main meals they ate in a day. For each main meal, subjects are asked how fast they ate, what they were doing while they ate, what food groups were included in their meals, and how much they ate. It also asks subjects if they ate any food outside of their main meals, and then asks how many times they eat each type of food.

Duration: 10 minutes.

Action Plan Creation – Participants in the **concurrent cohort** of the HEART pilot study will fill out the Action Plan Worksheet, the APA-10, and the APIS-5 as regularly scheduled for the main MINDFUL-PC study. Participants in the **alumni cohort** of the HEART study will fill out the Action Plan Worksheet and the APA-10 at the end of HEART study Week 3. They will fill out the APIS-5 at the end of HEART study Weeks 4 and 5.

Action Plan Creation Duration: 20 minutes

[figure not shown]
Action Plan Initiation Survey Duration: 5 minutes

Behavioral Tasks

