Because the data collected from the Argus app is not relating to sensitive information such as illegal activity or addiction, we determined it is not necessary to require secure Wi-Fi options for participants throughout the study. However, we will inform participants about the risks of using unsecure Wi-Fi and encourage them to use only secure Wi-Fi while using the smartphone app.

The study staff will notify the IRB if there is a need to have communication with the device or application manufacturers. While all smartphones have GPS capability, the research team will not be accessing any information related to current patient location that can be accessed through the GPS data. Similarly, while the photo function will be used to take pictures of food, the research team and the smartphone application will not be accessing any photos in the participant's photo album. The orientation protocol will show participants how to disable the smartphone's application's access to GPS, the participant's photo album, and to manage updates and push notifications. The study team will limit its use of data to only specified data points as outlined in the HEART study survey battery.

Data collected from the Kardia Mobile App will be written down by hand on a handout that is filed in the study binder which is locked in a double-locked cabinet and then entered into the secure CHA REDCap database by a member of the study staff.

Each participant will be given a HEART-study-specific study number, which will be used as an identifier in the Kardia Mobile app, the SART task, and the hypothetical discounting task (HDT). Therefore, the software developers will not have access to any identifiable data about any of the participants.

The SART task and HDT task will be done on a study laptop that is password secured and kept in a double-locked cabinet in the research office, accessible only by staff who have been IRB approved on the study. The data collected will be kept in an additional password protected file during retrieval and then transferred to a secure CHA drive after each study session is complete.

D.1.b. Database Protection:

Subject informed consent, screening forms, scantron sheets, and MTPC course documents will be stored in locked file cabinets within a locked office at Cambridge Health Alliance.

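### HEART entry requires willingness to photograph food and drink, but no photograph task is scheduled, paid for or analysed, so the clause can exclude willing patients for no return

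*Combined protocol and SAP*

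**What the plan says.** Two places treat food photographs as part of HEART.

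- C.1.c.3, item 3, adds to the daily-tracking condition that the participant must "be willing to take pictures of their food and drink intake".
- D.1.a, on privacy, says "while the photo function will be used to take pictures of food", and then gives an assurance that the participant's photo album will not be accessed.

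The places that set out what HEART participants do contain no such task.

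- Appendix A, Table 4 (concurrent cohort) has daily rows for "Smartphone app/accelerometer-based daily activity tracking", the FAST questionnaire, a practice diary and a resource-use diary, plus two behavioral visits.
- The task list in C.3.d.4 and the battery in C.3.f.7 cover the same ground. Diet is captured by FAST: "The food tracking portion asks subjects what main meals they ate in a day".
- The concurrent-cohort eligibility list in C.3.d.4 has no photograph clause. It asks that "participants must be willing to attend the two behavioral task sessions" and that the "participant must be willing to fill out online surveys at home".

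For recruitment, D.3.b.2 and D.4.c aim for 70 HEART participants and allow for as few as 47.

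**The concern.** An inclusion criterion decides who may enter. At the HEART consent session (C.3.d.4, repeated in D.5.d), a doctoral-level staff member goes through the criteria, and an interested person who does not agree to the requirements is excluded. If the C.1.c.3 list is the one applied, someone content with every scheduled HEART task can be turned away for declining photographs alone.

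The planned HEART correlations depend on the number recruited, and D.4.c already provides for recruitment below target. An entry condition with no matching measurement can only reduce the pool. The privacy section also describes image collection that the procedures do not contain.

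**Working it through.** **Step 1: look for the photograph task in the current text.**

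- Task list, C.3.d.4: practice and resource diaries, activity tracking, FAST, behavioral tasks. No photographs.
- Battery, C.3.f.7: activity app, possible wristband, FAST, action-plan forms, behavioral tasks. No photographs. This section addresses both the alumni and the concurrent cohorts.
- Analyses, C.5.b and D.4.c: step count, active periods, sleep duration, mindfulness practice and nutritional habits. No photograph-derived variable is named.
- Payments, D.7 (concurrent cohort): pre-visit 30 + Part 0 21 + Parts 1 and 2 84 + post-visit 30 + bonus 30 = $195. The 21 is 3 items × $7 and the 84 is 3 items × $28: mindfulness tracking, activity tracking and FAST. The total closes with no photograph item.
- Schedule, Appendix A, Table 4 (concurrent cohort): no photograph row.

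D.1.a itself limits the data used to the points set out in the HEART battery, and photographs are not among them. The version 1.17 change log has the entry "Remove daily diet picture tracking with a mobile app from the HEART study measures". That fits a leftover clause, but it is background only. The point rests on the current sections above.

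**Step 2: reproduce the plan's own HEART figures.**

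D.4.c gives 80% power at alpha 0.05 for r = 0.33 with 70 participants and r = 0.4 with 47. It does not say whether the test is one- or two-sided, so I assume two-sided. By the Fisher z approximation:

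n = ((1.96 + 0.8416) / atanh(r))² + 3

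- r = 0.33: n = 69.8, rounded up to 70
- r = 0.40: n = 46.7, rounded up to 47

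Both stated figures reproduce.

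**Step 3: illustrate a loss.**

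The documents give no share of candidates who would decline photographs. Assume 10-20% of the target of 70 and no replacement. The detectable correlation at 80% power is r = tanh(2.8016 / √(n − 3)).

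| Loss | n | Detectable r | Power for r = 0.33 |
|---|---|---|---|
| none | 70 | tanh(2.8016/√67) = 0.330 | 80.1% |
| 10% | 63 | tanh(2.8016/√60) = 0.347 | 75.7% |
| 20% | 56 | tanh(2.8016/√53) = 0.367 | 70.4% |

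Both reduced sizes stay above the plan's own minimum of 47.

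**The case against.** The best defence is that this is leftover wording in an optional pilot and that nothing shows it had any effect. Much of that stands.

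- **Actual exclusions.** A reader might infer that patients were screened out. No document reports this. The concurrent-cohort list in C.3.d.4 has no photograph clause, so the outcome depends on which list staff apply.
- **Whether photographs are taken.** D.1.a still says they are, the HEART aim in A.2.a speaks of diet trackers, and the end of Appendix A leaves room for diet-tracking applications. The text therefore conflicts with itself. But none of these places sets a photograph task, a schedule, a payment or an analysis.
- **Table 4 as evidence.** It covers only the concurrent cohort and omits the action-plan forms, so its silence alone is weak. The cross-cohort battery in C.3.f.7 is the stronger evidence.
- **Conflicting rules on behavioral sessions.** A reader might infer that the two eligibility lists also contradict each other here. The C.3.d.4 list is specific to the concurrent cohort, so its extra condition does not conflict with the general list in C.1.c.3.
- **Size.** The target of 70 is drawn from a much larger planned trial population (434-1,000), so people who decline may be replaced. Taking a further loss off 47 would count the shortfall twice, because D.3.b.2 already calls 47 the absolute minimum.
- **Selection.** A reader might infer that the clause favours people engaged with diet and so tilts the comparison of activity with diet goals. Participants already have to complete a daily food questionnaire, and nothing in the documents shows extra selection from the photograph clause.

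What remains is that the clause is an operative entry rule which staff are told to review, and it has no procedure behind it.

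**Conclusion.** The inconsistency is real and small. C.1.c.3 and D.1.a refer to food photographs that the HEART task list, battery, analyses, payments and concurrent-cohort schedule do not contain. Because the clause sits in an inclusion criterion, it can affect who enters, which makes it slightly more than an editorial slip. The documents support saying that patients can be excluded needlessly, not that they were.

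The number affected is unknown. On an assumed 10-20% unreplaced loss from 70, the detectable correlation moves from 0.33 to about 0.35-0.37, a modest change that would shrink or vanish if those who decline are replaced. The sample size, endpoints and analysis of the main randomised trial are unaffected.

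**What to change.** - In C.1.c.3, item 3, delete the closing requirement to "be willing to take pictures of their food and drink intake", with the conjunction before it.
- In D.1.a, delete only the clause "while the photo function will be used to take pictures of food". Keep the assurance that photo albums are not accessed.
- Check the HEART consent wording and align it.

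Do not replace the two eligibility lists with one merged list taken from C.3.d.4. Criterion 1 of C.1.c.3 (current enrolment in, or completion of, the main study) should stay. The two behavioral sessions should remain a condition for the concurrent cohort only: C.5.b, D.3.b.2 and D.4.c still count 40 alumni among the 70, and those visits are described only on the concurrent-cohort timetable.

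The cost is two short deletions and a consent check. No data are lost, because no photographs are scheduled or analysed.
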